7.2 Discussion of Design

Since CHM is a bilateral disease, this open-label study is being conducted to assess the safety of AAV2-REP1 administered to both eyes of subjects with CHM. All enrolled subjects will receive treatment with AAV2-REP1 at a dose of 1×10^{11} AAV2-REP1 gp/eye. Bilateral sub-retinal administration of AAV2-REP1 was explored in a pre-clinical toxicology study in rats and was found to be well tolerated and not associated with drug-related AEs. Furthermore, sequential sub-retinal administration of an AAV2 vector to the contralateral eye in children and adults with Leber's congenital amaurosis was demonstrated to be safe and efficacious, irrespective of baseline immune status ([Bennett, Wellman et al. 2016](#)).

The planned sample size (approximately 60 subjects, with a total of 120 treated eyes) is considered sufficient to characterise the immunological, vector shedding, and safety profiles of bilateral retinal gene therapy with AAV2-REP1. A prospective trial period of at least 12 months following the administration of AAV2-REP1 in each eye is considered a sufficient period of time to observe any treatment related safety concerns.

The dose of vector being employed in this study is based on previous clinical trials using the AAV2 vector with a chicken β actin (CBA) promoter ([Maguire, High et al. 2009](#), [MacLaren, Groppe et al. 2014](#)), and the Phase 1 / 2 investigator-sponsored clinical studies in which AAV2-REP1 was administered to subjects with CHM ([MacLaren, Groppe et al. 2014](#)) ([Dimopolous, Hoang et al. 2018](#), [Fischer, Ochakovski et al. 2018](#), [Lam, Davis et al. 2019](#)).

Application of AAV2-REP1 to the retina requires retinal detachment following vitrectomy. The risks of vitrectomy and retinal detachment are summarized in [Section 5.4](#).

In line with guidance from regulatory agencies, the treatment intervals were chosen to comprehensively characterise the immunological profile following bilateral, sequential AAV2-REP1 treatment, and to reflect real-world application of gene therapy. As noted, both preclinical data with AAV2-REP1, and clinical data with sub-retinal administration of an AAV2 vector in subjects with Leber's congenital amaurosis, support bilateral administration of AAV2-REP1 in humans.

To minimise inflammation resulting from surgery, and potential or unexpected immune responses to vector/transgene, all subjects will be given a course of oral prednisone/prednisolone, initiated 2 days prior to surgery on both SE1 and SE2. The regimen has been modified from the 17-day protocol established in the Philadelphia AAV gene therapy clinical trial ([Maguire, Simonelli et al. 2008](#)), with the allowance of an extra 4 days for tapering the dose at the end of the course. The corticosteroid regimen is 1 mg/kg/day (for a maximum of 80 mg/daily) prednisone/prednisolone for a total of 10 days (beginning 2 days before the vector injection, on the day of injection, and then for 7 days); followed by

0.5 mg/kg/day for 7 days; 0.25 mg/kg/day for 2 days; and 0.125 mg/kg/day for 2 days (21 days in total). See [Section 9.8](#) for details.

8 SELECTION AND WITHDRAWAL OF SUBJECTS

The study will enroll approximately 60 subjects with CHM, for a total of 120 treated eyes (see [Section 13.1](#) for discussion of the sample size determination).

8.1 Inclusion Criteria

During the Screening Period, subjects will be found eligible for study participation if they meet all of the following inclusion criteria.

1. Are willing and able to give informed consent for participation in the study to have both eyes treated
2. Are male and ≥ 18 years of age
3. Have documentation of a genetically-confirmed diagnosis of CHM
4. Have active disease clinically visible within the macular region of both eyes
5. Have a BCVA of ≥ 34 ETDRS letters (20/200 or better Snellen acuity) in both eyes, or in the untreated eye, if the other eye was previously treated with AAV2-REP1*

*If previously treated with AAV2-REP1 in an antecedent study, subjects may be eligible for participation following Sponsor approval.

6. For subjects who received treatment with AAV2-REP1 in an antecedent study, have biological samples available to complete an adequate immunology profile

8.2 Exclusion Criteria

During the Screening Period, subjects will be found not eligible for study participation if they meet any of the following exclusion criteria.

1. Have a history of amblyopia or inflammatory disorder in either eye
2. Are unwilling to use barrier contraception methods or abstain from sexual intercourse for a period of 3 months following treatment with AAV2-REP1 in either eye
3. Have had previous intraocular surgery performed within 3 months of the Screening Visit in either eye
4. Have any other significant ocular or non-ocular disease/disorder which, in the opinion of the Patient Eligibility Review Committee or Investigator, may either put the subjects at risk because of participation in the study, or may influence the results of the study or the subject's ability to participate in the study. This includes but is not limited to a potential subject:
 - with a contraindication to oral corticosteroid (e.g., prednisolone/prednisone)
 - with clinically significant cataract in either eye
 - who, in the clinical opinion of the Patient Eligibility Review Committee or Investigator, is not an appropriate candidate for sub-retinal surgery (see the Patient Eligibility Review Plan)
5. Have participated in another research study involving an investigational product in the past 12 weeks or received a gene/cell-based therapy at any time previously, except if treated within an antecedent study with AAV2-REP1

8.3 Subject Withdrawal Criteria

Each subject has the right to withdraw from the study at any time without prejudice. In addition, the Investigator may discontinue a subject from the study at any time if the Investigator considers it necessary for any reason, including:

- Significant protocol deviation
- Significant non-compliance with study requirements
- AE which results in an inability to continue to comply with study assessments
- Lost to follow up
- Other (to be specified on the electronic case report form [eCRF]).
 - If severe ocular inflammation (e.g. endophthalmitis) or any other post-operative sequela that is unresponsive to treatment occurs in SE1, the second eye should not be treated. However, Period 1 should be continued for monitoring of safety for the duration of the study.
 - At the discretion of the Investigator, if a persistent post-operative complication or poor visual function outcome presents post-operatively in SE1, the second eye may not be treated. However, Period 1 should be continued for monitoring of safety for the duration of the study.

In the event that a subject discontinues the study, the reason for withdrawal is to be recorded in the eCRF, and the site should use every reasonable effort to ensure that an end of trial (ET) Visit is conducted as outlined in the Schedule of Study Procedures ([Table 1](#)). If the subject is withdrawn due to an AE, the Investigator will arrange for follow-up until the event has resolved, subsided, stabilised, or the subject withdraws consent or is lost to follow-up. For subjects who withdraw consent, data will be collected through their last available study visit. Subjects withdrawn from the study may possibly be replaced. Subjects who withdraw from the study must undergo the ET Visit assessments. See [Table 1](#).

Withdrawal from the study will not result in the exclusion of a subject's data acquired up to the point of withdrawal.

9 STUDY TREATMENT

9.1 Treatments Administered

Eligible subjects will undergo vitrectomy and retinal detachment in each eye. At Period 1, Visit 1 (Day 0, the Injection Day Visit for SE1), subjects will receive in SE1 a sub-retinal injection of up to 0.1 mL of study drug containing 1×10^{11} AAV2-REP1 gp. At Period 2, Visit 1 (Day 0, the Injection Day Visit for SE2), subjects will receive in SE2 up to 0.1 mL of AAV2-REP1 via sub-retinal injection.

9.2 Description of Study Drug

The AAV2 vector contains recombinant human cDNA encoding REP1 (AAV2-REP1). The vector genome (AAV2-CBA-hREP1-WPRE-BGH) is comprised of a strong constitutive expression cassette, a hybrid CBA promoter, the human cDNA encoding REP1, a modified woodchuck hepatitis post-transcriptional regulatory element (WPRE) sequence, and a bovine growth hormone polyadenylation (BGH-polyA) sequence flanked by AAV2 inverted terminal repeats. The cDNA fragment was originally isolated from a human retinal cDNA library from unaffected individuals.

The AAV2-REP1 drug product is formulated in a sterile, 20 mM Tris-buffered solution, pH 8.0, and contains 1 mM MgCl₂, 200 mM NaCl and 0.001% PF68. The drug product is a clear to slightly opalescent, colourless, sterile-filtered suspension with a target concentration of 1×10^{12} gp/mL.

9.3 Packaging, Labeling, and Storage

AAV2-REP1 is currently supplied in sterile single-use vials, stoppered and capped. A total of 0.3 mL vector suspension will be supplied for each eye to be treated. Prior to shipment, each vial will be placed in a labeled secondary container. The drug product is to be stored at <-60°C (<-76°F) in a controlled access, temperature monitored freezer.

The GTMP will be labeled in compliance with regulatory standards.

9.4 Vitrectomy Procedure and Injection of AAV2-REP1

Injection of AAV2-REP1 is to be performed by an appropriately qualified and experienced retinal surgeon. All surgeons must have completed surgical training and obtained certification by NightstaRx to perform the study procedure, before treating a study participant. Training conducted as part of a previous AAV2-REP1 clinical trial or alternative AAV NightstaRx-sponsored gene therapy trial, can be used as the basis for approval.

Due to the complexity and unpredictability of detaching the retina in CHM, in which the retina and choroid can be extremely thin and fused in places, a modification to the technique of sub-retinal gene therapy has been developed. This involves performing the vector delivery in 2 steps after vitrectomy. An advantage of a 2-step procedure is that any unexpected complications of retinal detachment can be managed conservatively, minimising concerns about the vector escaping into the vitreous. Further, the injection could be deferred until a later date if, for instance, a macular hole was created which required treatment with gas. Also, since the volume of fluid required to detach the fovea is variable, by removing the vector from the first step, a precise consistent dose in terms of genome particles can still be applied into the sub-retinal space.

Initially, subjects will undergo a standard vitrectomy and detachment of the posterior hyaloid in the respective study eye ([Figure 2](#)). All surgeries will be conducted using the standard BIOM vitrectomy system. A 23-gauge sutured approach is usually favored to avoid any potential risks of wound leakage. The retina will be detached with 0.1-0.5 mL of balanced salt solution (BSS) injected through a 41-gauge sub-retinal cannula connected to a vitreous injection set.

[figure not shown]
In the second step of the procedure, the BSS cannula is removed from the eye and AAV2-REP1 is prepared for injection. A dose of up to 1.0×10^{11} gp of AAV2-REP1 is injected into the sub-retinal space through the same entry site. To improve visualization of the vector and facilitate dosing, surgeons are given the option of adding a minute quantity of trypan blue ophthalmic solution (~6 μ L) to the vector solution. See the GEMINI Surgical Manual for further details.

Prior to administration, the vector needs to be primed in the 1-mL syringe to avoid formation of air bubbles, and a connector is used so that the 1-mL syringe can be connected to the constant pressure line of the vitrectomy machine. The sub-retinal injection will target any area of the macula, but also include the fovea, if possible. In each case, the vector is injected so that the sub-retinal fluid overlies all edge boundaries of the central region that has yet to undergo chorioretinal degeneration, as identified by fundus AF. After wound closure, care will be taken to dispose of all irrigating fluids that may have passed through the eye to limit potential vector spread. See the GEMINI Surgical Manual for further details.

Subjects will be carefully monitored for the occurrence of AEs peri- and post-operatively. All AEs, irrespective of relationship to the study drug and/or the surgical procedure, will be captured in the subject's medical record and reported in the eCRF.

Air fluid exchange during pars plana vitrectomy is not required for this surgical procedure. However, if an air fluid exchange is considered necessary, patients must be instructed to avoid air travel, travelling to high elevations or scuba diving until the air bubble has completely dissipated from the eye. It may take one week or more following injection for the air bubble to dissipate. A change in altitude while the air bubble is still present can result in irreversible vision loss. The dissipation of the air bubble should be verified through meticulous ophthalmic examination.

Figure 2 **Vitrectomy and Sub-Retinal Injection of AAV2 Vector**

(A) A standard vitrectomy through the BIOM operating system to remove the vitreous gel is followed by (B) a 2- step procedure: 1) retinal detachment by injection of BSS; 2) injection of a volume of up to 0.1 mL vector suspension through a 41-gauge cannula into the sub-retinal space.

9.5 Randomisation

Not applicable for this study.

9.6 Study Masking

Not applicable for this study.

9.7 Study Drug Accountability

Records of the receipt and dispensing of study drug will be kept by each study centre until the end of the study to provide complete accounting of all used and unused study drug.

Dispensation logs will be checked by the Sponsor (or its designee). Study centres will destroy all used vials in accordance with local regulations, and will return all unused study drug to the Sponsor (or its designee) at the end of the study. Final drug accountability will be verified by the Sponsor (or its designee).

9.8 Concomitant Therapy

Subjects cannot have participated in another research study involving an investigational product in the past 12 weeks or received a gene/cell-based therapy at any time previously, except if treated within another study with AAV2-REP1.

Throughout the study, subjects may be prescribed any concomitant medications, procedures, or treatments deemed necessary to provide adequate supportive care. Details of concomitant medications, procedures and/or treatments will be collected during the Screening Period and updated at every study visit (including the ET Visit, if applicable). Concomitant medications (including oral corticosteroid), procedures and/or treatments taken during the study are to be recorded in the subject's medical records and eCRF; an exception to this is any medication used in the course of conducting study assessments (e.g., ophthalmic dyes, topical anaesthesia, dilating eye drops).

In addition, all subjects will be prescribed a course of oral corticosteroids.

The oral prednisone / prednisolone regimen has been modified from the 17-day protocol established in the Philadelphia voretigene neparvovec-rzyl gene therapy clinical trial for treatment of patients with confirmed bi-allelic RPE65 mutation-associated retinal dystrophy ([Maguire, Simonelli et al. 2008](#)), with the allowance of an extra 4 days for tapering the dose at the end of the course. The corticosteroid regimen is 1 mg/kg/day prednisone/prednisolone (not to exceed 80 mg/daily) for a total of 10 days (beginning 2 days before the vector injection, on the day of injection, and then for 7 days); followed by 0.5 mg/kg/day for 7 days; 0.25 mg/kg/day for 2 days; and 0.125 mg/kg/day for 2 days (21 days in total; Study Day (SD) -2 through SD18). This regimen is outlined in detail below.

Full Corticosteroid Regimen

Prednisone or prednisolone administered as follows:

- SD -2 through SD 7 (10 days): 1 mg/kg by mouth daily (not to exceed 80 mg/daily)
- SD 8 through SD 14 (7 days): 0.5 mg/kg/day by mouth daily
- SD 15 through SD 16 (2 days): 0.25 mg/kg/day by mouth daily
- SD 17 through SD 18 (2 days): 0.125 mg/kg/day by mouth daily

For SE1, the Full Corticosteroid Regimen should be initiated as described.

For SE2 surgeries that occur on day 21 or later, the Full Corticosteroid Regimen should be initiated as described, beginning 2 days before the scheduled SE2 surgery.

If SE2 is to be performed prior to Study Day 21, then the Full Corticosteroid Regimen should be initiated 2 days prior to the scheduled surgery for SE2, and this will supersede the steroid taper in progress for SE1. The full 21 days of treatment will then be completed for SE2.

Details of corticosteroid usage will be captured by each subject in a diary card.

If inflammation is observed in the study eye, and in the opinion of the Investigator additional treatment with corticosteroid medication is indicated, corticosteroid therapy may be increased during the taper period (to a maximum of 1 mg/kg/day), may be reinitiated following completion of the taper, and/or may be supplemented by intraocular corticosteroids.

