Vanderberghe, L. H. and A. Auricchio (2012). "Novel adeno-associated viral vectors for retinal gene therapy." Gene Ther **19**(2): 162-168.

Biogen MA Inc.
[name]
[name]
United States

Biogen Idec Research Limited
[name]
United Kingdom

AMENDMENT SUMMARY

Biogen Protocol 273CH203 (Formerly NSR-REP-02)

An Open-Label Safety Study of Retinal Gene Therapy for Choroideremia with Bilateral, Sequential Administration of Adeno-Associated Viral Vector (AAV2) Encoding Rab Escort Protein 1 (REP1)

GEMINI Study

For Global Protocol Amendment: Version 6.0

Date: 12 November 2020

EUDRA CT Number: 2017-002395-75

Version 6.0 of the protocol has been prepared for this amendment, which supersedes Version 5.0 dated 30 April 2020.

CONFIDENTIAL

The information contained herein may not be used, disclosed, or published without the written consent of Biogen MA Inc.

PRIMARY REASON FOR AMENDMENT

The primary reason for this amendment to Protocol 273CH203 (NSR-REP-02) is for safety of participants: a maximum dose of 80 mg daily of corticosteroid has been added to the corticosteroid regimen.

New text is shown in **bold** type; deleted text is shown with a ~~strikethrough~~.

The synopsis was revised to reflect changes made throughout the protocol.

Section 7.2 Discussion of Design

Now reads:

The corticosteroid regimen is 1 mg/kg/day (**for a maximum of 80 mg/daily**) prednisone/prednisolone for a total of 10 days (beginning 2 days before the vector injection, on the day of injection, and then for 7 days); followed by 0.5 mg/kg/day for 7 days; 0.25 mg/kg/day for 2 days; and 0.125 mg/kg/day for 2 days (21 days in total).

Rationale: A maximum dose of 80 mg daily of corticosteroid has been added to the corticosteroid regimen.

This change also affects:

Section 9.8, Concomitant Therapy

The corticosteroid regimen is 1 mg/kg/day prednisone/prednisolone (**not to exceed 80 mg/daily**) for a total of 10 days (beginning 2 days before the vector injection, on the day of injection, and then for 7 days); followed by 0.5 mg/kg/day for 7 days; 0.25 mg/kg/day for 2 days; and 0.125 mg/kg/day for 2 days (21 days in total; Study Day (SD) -2 through SD18).

Full Corticosteroid Regimen

Prednisone or prednisolone administered as follows:

- SD -2 through SD 7 (10 days): 1 mg/kg by mouth daily (**not to exceed 80 mg/daily**)
- SD 8 through SD 14 (7 days): 0.5 mg/kg/day by mouth daily

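### The 80 mg/day corticosteroid maximum added in Version 6.0 is missing from the rescue sentence in Protocol Section 9.8, so subjects above 80 kg can be raised past it during the taper

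*Protocol*

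**What the plan says.** The Amendment Summary for Version 6.0 gives as the primary reason that the change "is for safety of participants: a maximum dose of 80 mg daily of corticosteroid has been added to the corticosteroid regimen".

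In the current protocol the cap appears three times, each time tied to the 1 mg/kg step:

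- Section 7.2: "The corticosteroid regimen is 1 mg/kg/day (for a maximum of 80 mg/daily) prednisone/prednisolone for a total of 10 days".
- Section 9.8, narrative: "The corticosteroid regimen is 1 mg/kg/day prednisone/prednisolone (not to exceed 80 mg/daily) for a total of 10 days".
- Section 9.8, Full Corticosteroid Regimen: "SD -2 through SD 7 (10 days): 1 mg/kg by mouth daily (not to exceed 80 mg/daily".

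The taper steps that follow carry no milligram limit. The first reads "SD 8 through SD 14 (7 days): 0.5 mg/kg/day by mouth daily".

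Section 9.8 then covers extra treatment when the Investigator sees inflammation and judges it necessary: "corticosteroid therapy may be increased during the taper period (to a maximum of 1 mg/kg/day), may be reinitiated following completion of the taper". The same sentence also allows intraocular corticosteroids as a supplement. It gives no milligram figure and no reference back to the cap. Section 10.1 and footnote m of Table 1 send the reader to Section 9.8 and add no limit of their own.

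**The concern.** A 1 mg/kg dose capped at 80 mg is restricted only in subjects heavier than 80 kg, so the cap protects exactly that group. The rescue sentence, in the same section, sets a separate ceiling that lets the same group go higher. A heavier subject could have his planned peak dose held down for safety and then receive more than that peak during the taper, without breaching the rescue sentence.

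Re-initiation after the taper is looser still. The 1 mg/kg/day limit is attached to an increase during the taper, and no dose is stated for a restarted course. Restarting the Full Corticosteroid Regimen would bring the cap with it, but the sentence does not say that this is what is meant.

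What is at stake is a dose limit for a systemic drug that every subject takes around each surgery. The trial's inference is not affected.

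**Working it through.** **Inputs**

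- Cap: 80 mg/day, on the 1 mg/kg step only (Protocol 7.2 and 9.8).
- Rescue ceiling during the taper: 1 mg/kg/day (Protocol 9.8).
- Taper steps: 0.5, 0.25 and 0.125 mg/kg/day (Protocol 9.8).
- Body weight: recorded to calculate the corticosteroid dose (Table 1, footnote f), but no weights are given. The weights below are assumptions.

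**Regimen length.** Study Days -2 to 7 are 10 days, 8 to 14 are 7, 15 to 16 are 2, and 17 to 18 are 2. The total is 10 + 7 + 2 + 2 = 21 days, which matches the stated length. The taper is 7 + 2 + 2 = 11 days.

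**Weight at which the ceilings part.** 80 mg ÷ 1 mg/kg = 80 kg. This follows from the text alone.

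**Is the scheduled taper also a problem?** Its highest step reaches 80 mg at 80 ÷ 0.5 = 160 kg, so for practical purposes it is not. The gap lies in the rescue sentence.

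**Rescue ceiling by weight.** As worded it is 1 × weight. With the cap it would be the smaller of 1 × weight and 80 mg. The largest excess over the whole taper is 11 × (weight − 80).

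| Assumed weight (kg) | Rescue ceiling as worded (mg/day) | With the cap (mg/day) | Daily excess | Largest excess over 11 days (mg) |
|---|---|---|---|---|
| 70 | 70 | 70 | 0 | 0 |
| 80 | 80 | 80 | 0 | 0 |
| 90 | 90 | 80 | 10 mg (12.5%) | 110 |
| 100 | 100 | 80 | 20 mg (25%) | 220 |
| 120 | 120 | 80 | 40 mg (50%) | 440 |

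**Example at 100 kg.** The scheduled taper totals 7 × 50 + 2 × 25 + 2 × 12.5 = 425 mg. Rescue at the ceiling on every taper day totals 11 × 100 = 1,100 mg as worded and 11 × 80 = 880 mg if capped, a difference of 220 mg.

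The last column of the table is an upper bound. It assumes rescue at the maximum dose on each day from 8 to 18.

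**The case against.** The strongest reply is that the amendment did what it said. It added the maximum to the corticosteroid regimen, and Section 9.8 defines that regimen as the planned course. Rescue is a different matter: it treats inflammation already seen in an operated eye. Section 5.4 lists inflammation as a potential risk, and Section 8.3 bars treatment of the second eye after severe inflammation in the first that does not respond to treatment. A sponsor could reasonably leave the Investigator more room there. Alternatively, the rescue parenthesis can be read as a return to the first step of the regimen, cap included, and then there is no gap.

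Both readings are possible, and neither is written down. They also point in opposite directions: one exempts rescue from the cap and the other applies the cap to it. Two sites could therefore dose the same heavy subject differently and both believe they were compliant. A deliberate exemption would also be an odd one. The rescue ceiling equals the planned peak for everyone at or below 80 kg and exceeds it only in the subjects whom the cap restricts. That looks more like a clause missed in the amendment than a considered trade-off.

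Two parts of the reply stand:

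- The affected group is probably small. Contraindication to oral corticosteroid is an exclusion, steroid use is recorded by diary and in the eCRF, and adverse events are monitored at every visit.
- Section 9.8 also permits any concomitant medication needed for supportive care. Amending the rescue sentence would therefore not create an absolute ceiling. It would make the specific rule that sites follow for steroid escalation agree with the safety limit.

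**Conclusion.** The concern holds. As worded, Section 9.8 allows oral rescue above 80 mg/day during the taper for any subject heavier than 80 kg, and it leaves the dose of a re-initiated course unstated. That the wording has this effect is certain. Whether the sponsor intended it cannot be settled from the documents.

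The practical effect is limited to subjects above 80 kg with observed inflammation whose Investigator raises the oral dose beyond 80 mg. How many that would be is unknown. The 12.5% to 50% range rests on assumed weights of 90 to 120 kg, and the cumulative figures of 110 to 440 mg further assume maximum-dose rescue throughout the taper. It is worth correcting because it leaves the stated purpose of the current version incomplete and the remedy is small.

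**What to change.** In the rescue sentence of Section 9.8, extend the parenthesis to read: *to a maximum of 1 mg/kg/day, not to exceed 80 mg/day*. State that the same limit applies to any re-initiated oral course. If the sponsor does intend rescue to be exempt from the cap, the sentence should say so.

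The clinical cost is a lower oral rescue ceiling for subjects above 80 kg. Intraocular corticosteroid, already allowed in that sentence, remains available. Sections 7.2 and 10.1 and footnote m of Table 1 already refer to Section 9.8, so aligning the rescue rule needs no edit elsewhere. The change can go in the next amendment or a clarification letter. It needs no new data and no SAP change.
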